6.2.4. Exploratory Endpoints

The following exploratory endpoints will be examined by descriptive statistics:

- Correlative laboratory studies of subjects including an analysis of mutational status of at least 53 genes known to be affected in acute leukemias will be performed, and evaluation of any potential relationship with the presence or absence of mutations and response will be assessed. This panel has been validated using a next generation sequencing (NGS) platform for the detection of frequently reported mutations in our CLIA-certified molecular diagnostics laboratory.
- Proportion of subjects achieving a major or minor cytogenetics response during study bone marrow assessments per IWG-2006 criteria.
 - o Major: Disappearance of cytogenetic abnormality
 - o Minor: $\geq 50\%$ reduction in abnormal metaphases out of 20 analyzable metaphases
- Evaluation of the efficacy of eltrombopag (as determined by IWG-2006 criteria) based on IPSS risk classification system at diagnosis

- The number and frequency of platelet transfusions received during the treatment period will also be assessed
- To examine the relationship between clinical response with ferritin level and other markers of iron burden at study start, given recent data that the antileukemic effects of eltrombopag may be mediated through modulation of intracellular iron content.

6.3 Subsets

6.3.1. Full Analysis Set

The full analysis set will consist of all enrolled subjects. Subjects will be analyzed according to their treatment group. Analyses for demographics and baseline characteristics will utilize this analysis set.

6.3.2. Efficacy Analysis Set

The efficacy analysis set will consist of all enrolled subjects who have received at least one cycle of investigational product. Analysis for efficacy endpoints will utilize this analysis set.

6.3.3. Safety Analysis Set

The safety analysis set will consist of all enrolled subjects who received at least 1 dose of investigational product. Subjects will be analyzed according to the treatment actually received. Analysis for safety endpoints will utilize this analysis set.

7. Regulatory and Reporting Requirements

7.1. Informed Consent

Before a subject's participation in the clinical study, the investigator is responsible for obtaining written informed consent from the subject or legally acceptable representative after adequate explanation of the aims, methods, anticipated benefits, and potential hazards of the study and before any protocol-specific screening procedures or any investigational products are administered. A legally acceptable representative is an individual or other body authorized under applicable law to consent, on behalf of a prospective subject, to the subject's participation in the clinical study.

The acquisition of informed consent should be documented in the subject's medical records, and the informed consent form should be signed and personally dated by the subject or a legally acceptable representative and by the person who conducted the informed consent discussion. The original signed informed consent form should be

retained in accordance with institutional policy, and a copy of the signed consent form should be provided to the subject or legally acceptable representative.

7.2. Independent Ethics Committee/Institutional Review Board

A copy of the protocol, proposed informed consent form, other written subject information, and any proposed advertising material must be submitted to the IEC/IRB for written approval. A copy of the written approval of the protocol and informed consent form must be received by Novartis Oncology before recruitment of subjects into the study and shipment of investigational product.

The investigator must submit and, where necessary, obtain approval from the IEC/IRB for all subsequent protocol amendments and changes to the informed consent form. The investigator should notify the IEC/IRB of deviations from the protocol or serious adverse events occurring at the site and other adverse event reports received from GSK or Novartis Oncology, in accordance with local procedures.

The investigator will be responsible for obtaining annual IEC/IRB approval/renewal throughout the duration of the study. Copies of the investigator's reports and the IEC/IRB's continuance of approval must be sent to Novartis Oncology

7.3 Subject Confidentiality

The investigator must ensure that the subject's confidentiality is maintained. On all documents submitted to GSK or Novartis Oncology subjects should be identified by their initials and a subject study number only. Documents that are not for submission to Novartis Oncology (eg, signed informed consent forms) should be kept in strict confidence by the investigator.

In compliance with ICH GCP Guidelines, it is required that the investigator and institution permit authorized representatives of the company, of the regulatory agency(s), and the IEC/IRB direct access to review the subject's original medical records for verification of study-related procedures and data. Direct access includes examining, analyzing, verifying, and reproducing any records and reports that are important to the evaluation of the study. The investigator is obligated to inform and obtain the consent of the subject to permit named representatives to have access to his/her study-related records without violating the confidentiality of the subject.

7.4. Protocol Amendments and Study Termination

Protocol amendments, except where necessary to eliminate an immediate hazard to subjects, must be made only with the prior approval of Novartis Oncology. Agreement from the investigator must be obtained for all protocol amendments and amendments to the informed consent form. The IEC/IRB must be informed of all amendments and give approval. The investigator must send a copy of the approval letter from the IEC/IRB to

Novartis Oncology.

Both Novartis Oncology and the investigator reserve the right to terminate the study according to the study contract. The investigator should notify the IEC/IRB in writing of the study's completion or early termination and send a copy of the notification to Novartis Oncology.

Subjects may be eligible for continued treatment with investigational product by extension protocol or as provided for by the local country's regulatory mechanism. However, Novartis Oncology reserves the unilateral right, at its sole discretion, to determine whether to supply the investigational product, and by what mechanism after termination of the trial and before it is available commercially.

7.5. Study Documentation and Archival

The investigator should maintain a list of appropriately qualified persons to whom he/she has delegated study duties. All persons authorized to make entries and/or corrections on case report forms will be included on the Delegation of Authority Form.

Source documents are original documents, data, and records from which the subject's case report form data are obtained. These include but are not limited to hospital records, clinical and office charts, laboratory and pharmacy records, diaries, microfiches, radiographs, and correspondence. Case report form entries may be considered source data if the CRF is the site of the original recording (ie, there is no other written or electronic record of data). In this study, case report forms calculating IPSS may be used as source documents for IPSS risk category assignment.

The investigator and study staff are responsible for maintaining a comprehensive and centralized filing system of all study-related (essential) documentation, suitable for inspection at any time by representatives from Novartis Oncology and/or applicable regulatory authorities. Elements should include:

- Subject files containing completed case report forms, informed consent forms, and subject identification list
- Study files containing the protocol with all amendments, investigator's brochure, copies of prestudy documentation and all correspondence to and from the IEC/IRB and Novartis Oncology
- Proof of receipt, Investigational Product Accountability Record, Return of Investigational Product for Destruction, Final Investigational Product Reconciliation Statement, and all drug-related correspondence

In addition, all original source documents supporting entries in the case report forms must be maintained and be readily available. No study document should be destroyed without prior written agreement between Novartis Oncology and the investigator. Should

the investigator wish to assign the study records to another party or move them to another location, he/she must notify Novartis Oncology in writing of the new responsible person and/or the new location.

7.6. Serious Adverse Event Reporting (SAE):

See Section 6.2.2.1 for detailed information regarding SAE definitions.

It is the responsibility of the PI and the research teams to ensure serious adverse events are reported according to the Code of Federal Regulations, Good Clinical Practices, the protocol guidelines, the sponsor's guidelines, and Institutional Review Board policy.

All events occurring during the conduct of a protocol and meeting the definition of a SAE must be reported to the IRB in accordance with the timeframes and procedures outlined in "University of Texas M. D. Anderson Cancer Center Institutional Review Board Policy on Reporting Serious Adverse Events". Unless stated otherwise in the protocol, all SAEs, expected or unexpected, must be reported to Novartis Oncology, regardless of attribution (see Section 6.2.2.3). SAE reporting will be done according to 21 CFR 312.32(c)(1)(iv) ("Sponsor must report any clinically important increase in the rate of a serious adverse reaction over that listed in the protocol or investigator brochure.").

The descriptions and grading scales found in the revised NCI Common Terminology *Criteria for Adverse Events (CTCAE) version 4.0* will be utilized for adverse event reporting. (<http://ctep.cancer.gov/reporting/ctc.html>).

8. Statistical Considerations

8.1. Design and Sample Size

This is a two arm phase II study to evaluate the safety and efficacy of high dose eltrombopag for the treatment of MDS patients after experiencing hypomethylating agent (HMA) failure. The primary efficacy endpoint is the overall response rate (ORR) based on the IWG-2006 criteria, which include complete remission (CR), partial remission (PR), and major hematologic improvement (HI). Patients' overall response will be assessed after at least 2 cycles of treatment but no more than after 6 cycles; and each cycle is 28 days. A total of 46 patients will be enrolled by patient and treating physician preference into two arms: (A) eltrombopag only or (B) eltrombopag with continuation of the hypomethylating agent. All patients will be accrued from M. D. Anderson Cancer Center (MDACC).

Currently, there is no FDA approved agent for patients who have failed on hypomethylating agent, and therapeutic options are limited, particularly given the

increased age and frequent comorbidities of this population. In this proposed study, patients will be enrolled into one of two treatment arms. Treatment arm will be determined by patient and treating physician, taking into account patient experience with prior hypomethylating agent therapy. Arm A (eltrombopag only) or Arm B (eltrombopag with continuation of HMA). We anticipate that patients treated in Arm A will achieve an ORR of 15-20%, while patients treated in Arm B will achieve an improved ORR of 25%. Given the expected small difference (5-10%) between the two arms, the sample size needed to detect such a difference with enough statistical power will be too large to be accommodated in this small phase II trial. Therefore, our focus for this study is to assess the ORR in each arm separately using Simon's Minimax two-stage design²⁷.

8.2. Futility Monitoring

8.2.1. For patients treated in Arm A (eltrombopag alone), we assume a target ORR of 18% and a response rate of 5% or lower will be considered not desirable. With a 1-sided type I error rate of 10.3% and 80% power, we will enroll 15 patients in the first stage. If none of these patients achieve OR, the trial will be stopped. If 1 or more out of the first 15 patients have OR, accrual will continue until a total of 23 patients have been enrolled. At the end of the study, if 3 or more out of these 23 patients achieve OR, the treatment of eltrombopag alone will be considered efficacious and is worth further investigation. Under this Simon's Minimax two-stage design, the probability of early termination is 46.3% if the true ORR is 5% and the expected sample size is 19 patients.

For patients treated in Arm B (eltrombopag in combination with HMA), the target ORR is 25%, and a response rate of 5% or lower will be considered not desirable. With a 1-sided type I error rate of 3% and 85% power, we will enroll 12 patients in the first stage. If none of these 12 patients achieve OR, the trial will be stopped. If 1 or more out of the first 12 patients have OR, accrual will continue until a total of 23 patients have been enrolled. At the end of the study, if 4 or more of these 23 patients achieve OR, the treatment of eltrombopag in combination with HMA will be considered efficacious and is worth further investigation. Under this Simon's Minimax two-stage design, the probability of early termination is 54% if the true ORR is 5% and the expected sample size is 17 patients.

Patient enrollment will be suspended if for an arm the first-stage patients have been enrolled and none of these first-stage patients has OR. Accrual will resume if at least one OR is observed within 2 cycles among the first-stage patients for that arm.

8.2.2. The accumulating data will be summarized at regular intervals to provide an ongoing assessment of the safety and efficacy of eltrombopag in this population. Additional summaries of data may be provided for regulatory or publication activities.

8.3. Safety Monitoring

8.3.1. The method of Thall, Simon, and Estey²⁸ will be employed for interim safety monitoring. We assume a Beta (0.6, 1.4) prior distribution for the toxicity rate which has mean of 30%. For the purpose of safety monitoring, toxicities are defined as any grade 3 or greater clinically significant non-hematologic adverse events, attributed to the study drug.

The following Bayesian monitoring rule will be applied in each arm separately, starting from the 3rd patient and up to the total of 23 patients per arm. Specifically, an arm will be stopped early if

$$\text{Pr}[\text{toxicity rate} > 30\% | \text{data}] > 0.9$$

That is, if at any time during the study we determine that there is more than a 90% chance that the toxicity rate is more than 30% in a treatment arm, we will stop enrolling patients into that arm. If one arm is stopped due to severe toxicity, we will continue enroll patients into the other arm until the total accrual of 23 patients is reached or until the toxicity stopping boundary is crossed in that arm, whichever occurs first.

Stopping boundaries corresponding to this toxicity monitoring rule are displayed in the following table:

Number of patients evaluated	Recommend stopping if \geq toxicity observed
3-4	3
5-7	4
8-9	5
10-12	6
13-14	7
15-17	8
18-20	9
21-22	10

The operating characteristics of this toxicity monitoring rule are shown in the following table

True toxicity rate	Early stopping probability	Sample size percentile		
		25%	50%	75%
0.2	0.07	23	23	23

0.3	0.25	22	23	23
0.35	0.4	9	23	23
0.4	0.57	7	17	23

8.4 Statistical Analysis Plan

8.4.1. General Approach/Considerations

The final analysis will be performed when all data has been retrieved, entered, cleaned, locked and frozen. Descriptive statistics for demographic and baseline characteristics will be summarized for all enrolled subjects. For categorical variables, the number and percentage of subjects in each category will be summarized. Continuous variables will be summarized by n, mean, standard deviation, median, Q1 (25% percentile), Q3 (75% percentile), minimum and maximum values.

8.4.2. Analysis of Key Study Endpoints

The primary endpoint is overall response rate (ORR). The ORR in each arm will be evaluated along with the exact 95% confidence interval. Given the limited sample size, no formal comparison will be made between these two arms in terms of ORR.

Secondary endpoints include platelet response, durable platelet response, transformation to AML, incidence of bone marrow fibrosis, and time-to-event outcomes such as progression-free survival (PFS) and overall survival (OS). The probabilities of PFS and OS will be estimated using the method of Kaplan and Meier. The incidence rates of other binary secondary endpoints will be estimated, along with the exact 95% confidence intervals. Subjects that discontinue the study prior to having achieved a clinical response will be considered to have not had an event.

Patients receiving growth factors other than eltrombopag (erythropoietin, GM-CSF or G-CSF) will not be considered in the HI analysis for the time periods specified in Section 4.5.3 Supportive Care Guidelines. Hemoglobin levels and platelet counts collected from patients that have received a transfusion within the last 3 days will not be considered in the analysis.

Survival or times to failure and time to progression functions will be estimated using the Kaplan-Meier method. The two-sided log-rank test will be used to assess the differences of time to events between groups.

The total number of dose administrations, the average dose (mg), and the cumulative dose administered will be summarized by eltrombopag treatment group.

Blood chemistry and complete blood counts will be summarized by treatment group at each time point.

Additional exploratory analyses of the key study endpoints will be performed as deemed appropriate.

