Prognosis in HMA-failure patients is extremely poor. Jabbour et al⁹ report a median survival of merely 4 months in MDS patients with progressive disease after decitabine (Figure 1), and Prebet et al⁷ identified a similar median survival of 5.6 months in MDS patients with progressive disease after 5-azacytidine. There are no currently approved agents in the setting of HMA-failure MDS patients, and there are limited therapeutic options, particularly given the increased age and frequent comorbidities of this population.

As alluded to above, the platelet count in MDS patients is critically important, and impacts both treatment decisions and overall survival in the majority of MDS patients. Among 2410 patients with MDS referred to the MD Anderson Cancer Center, 67% had a platelet count $<100 \times 10^9/L$ at the time of their initial consultation, and even within the lower-risk MDS categories, over 10% of patients experience life-threatening thrombocytopenia ($<20 \times 10^9/L$) at presentation.¹⁰ Thrombocytopenia has been identified as an independent and adverse prognostic factor for overall survival in MDS at all stages.¹¹ An analysis of 892 primary MDS subjects identified a median survival in patients with platelet counts $< 100 \times 10^9/L$ of 27 months, compared to 60 months for patients with platelet counts $\geq 100 \times 10^9/L$.¹² Furthermore, the mainstay of treatment for thrombocytopenia in MDS patients, transfusions, are short-lived, and associated with transfusion reactions, allo-immunization, transmission of bacterial and viral infections, and have no impact on the underlying disease biology.

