4.2. Study Duration

4.2.1. All subjects must complete a screening visit, day 1 visits for each new cycle, an end of treatment visit and whenever possible, an end of study safety visit 28 days after the last dose of eltrombopag.

4.2.2. Patients may remain on study for up to 12 cycles if the patient demonstrates clinical benefit and no excessive toxicity (i.e. no clinically significant study-drug related grade ≥ 3 toxicity). Patients who are experiencing clinical benefit and have not experienced excessive toxicity may be eligible to continue therapy after discussion with the PI and the discussion documented in the patient's medical record.

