4.6. Duration of Therapy

Treatment is expected to continue until one of the following criteria applies:

- Lack of objective response after 2 cycles of therapy unless eltrombopag is considered to be of clinical benefit to the patient, or
- Clinically significant progressive disease, or
- Discontinuation of study drug for more than 6 weeks, or
- Intercurrent illness that prevents further administration of treatment, or
- Unacceptable adverse event(s), or
- Patient decision for study withdrawal, or
- General or specific changes in the patient's condition render the patient unacceptable for further treatment in the judgment of the investigator

Continuation of therapy beyond 12 months will be considered on a case-by-case basis for patients deriving clinical benefit after discussion with the PI and the discussion documented in the patient's medical record.

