6.2.3. Secondary Efficacy Endpoints

The key secondary endpoints for this study are:

- The incidence of transformation to AML by FAB during treatment period and follow-up
- The incidence and severity of bone marrow fibrosis during treatment period and follow-up
- Proportion of patients achieving a platelet response during treatment; and proportion of patients achieving a durable platelet response.
 - o Platelet IWG-2006: A complete response is defined as a platelet count $> 100 \times 10^9/L$; and a major response defined as an increase of platelet count by higher than $30 \times 10^9/L$.
 - o Durable platelet count: in which a hematologic improvement in platelets (HI-P) defined as either an increase $\geq 30 \times 10^9/L$ from patients with a baseline platelet count $\geq 20 \times 10^9/L$, or an increase from $< 20 \times 10^9/L$ to $\geq 20 \times 10^9/L$ and by at least 100%, present for ≥ 8 weeks.

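### AML transformation is planned as a crude proportion with no time horizon over very unequal observation, so it understates the risk by any fixed time; a cumulative incidence estimate should replace it

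*Combined protocol and SAP*

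**What the plan says.** Section 6.2.3 lists first among the key secondary endpoints "The incidence of transformation to AML by FAB during treatment period and follow-up". Neither this section nor Section 1.2 sets a time horizon.

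Section 8.4.2 gives PFS and OS Kaplan-Meier estimates. For the remaining secondary endpoints, AML transformation among them, it says "The incidence rates of other binary secondary endpoints will be estimated, along with the exact 95% confidence intervals". The next sentence reads "Subjects that discontinue the study prior to having achieved a clinical response will be considered to have not had an event" and is not limited to response endpoints. Further down come "Survival or times to failure and time to progression functions will be estimated using the Kaplan-Meier method" and "The two-sided log-rank test will be used to assess the differences of time to events between groups".

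Time to progression has no definition of its own. Section 6.2.1 defines PFS with progression or MDS death as the event. The documents nowhere mention cumulative incidence, competing risks or censoring rules.

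On length of observation, Section 4.6 ends treatment for "Lack of objective response after 2 cycles of therapy unless eltrombopag is considered to be of clinical benefit to the patient", and Section 4.2 says "Patients may remain on study for up to 12 cycles if the patient demonstrates clinical benefit", with extension possible. Section 5.5 and the study calendar place the last scheduled visit four weeks after the last dose. No later visit for AML or survival is scheduled, although follow-up and OS are named.

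**The concern.** Transformation is an event in time. A proportion with a binomial interval gives the same weight to a patient watched for about 12 weeks and one watched for a year, and it treats the first as transformation-free once observation stops. The result is not the risk by 6 months, by 12 months or by any other stated time, and the exact interval around it inherits that defect.

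The length of observation is tied to response, so the figure also shifts with the share of patients who stay on treatment. Two arms with the same AML hazard could report different proportions. If the sentence on patients who discontinue is applied to AML as well, the practice of counting them as event-free becomes explicit.

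AML transformation is the first secondary objective of a trial of a growth-factor-receptor agonist, and an understated figure would be read as reassurance.

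**Working it through.** The plan states no expected AML rate or precision, so there is no figure to reproduce. The following is an illustration.

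**Inputs from the documents**
- Short observation: 2 cycles × 28 + 28 days = 84 days = 2.76 months (Sections 4.6, 5.5).
- Long observation: 12 cycles × 28 + 28 days = 364 days = 11.96 months (Sections 4.2, 5.5).
- Share observed long: 15% to 25%, the span of the anticipated response rates (Section 8.1).
- Patients per arm: 23 (Section 8.2.1).
- Median survival after HMA failure with progressive disease: 4 and 5.6 months (Section 2.1).

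**Assumptions**
- Constant hazards, unrelated to response: a for AML, d for death without AML.
- True 12-month AML incidence 20%.
- Median time to death without AML 4, 5.6, 12 or 24 months. The range extends beyond the cited medians because Section 3.1 admits all IPSS groups.
- Observation ends at the safety visit.

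**Formulas**
- Cumulative incidence: CIF(t) = a/(a+d) × (1 − exp(−(a+d)t)), with d = ln 2 / median and a solved so that CIF(12) = 20%.
- Expected crude proportion = (1 − r) × CIF(84 days) + r × CIF(364 days), where r is the share observed long.
- 1 − Kaplan-Meier at 12 months with deaths censored = 1 − exp(−12a).

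**One case in full (median 5.6 months)**
- d = 0.1238 and a = 0.0377 per month.
- CIF(84 days) = 8.4%; CIF(364 days) = 20.0%.
- r = 15%: 0.85 × 8.4% + 0.15 × 20.0% = 10.1%.
- r = 25%: 0.75 × 8.4% + 0.25 × 20.0% = 11.3%.

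**All cases, true 12-month incidence 20%**

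| Median time to death without AML (months) | CIF at 84 days | Crude, r = 15% | Crude, r = 25% | 1 − KM, deaths censored |
|---|---|---|---|---|
| 4 | 9.8% | 11.3% | 12.4% | 43.5% |
| 5.6 | 8.4% | 10.1% | 11.3% | 36.4% |
| 12 | 6.5% | 8.5% | 9.9% | 27.2% |
| 24 | 5.7% | 7.9% | 9.3% | 23.5% |

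The crude figure lies between about 8% and 12% throughout. The shortfall is larger when mortality is lower, so it does not depend on the short survival medians. For a true incidence of 10% or 30%, the crude figure is 4% to 6% or 12% to 19%.

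**Which mechanism is at work.** A simulation of 400,000 patients, all followed to 12 months or death (median 5.6 months), gave a crude proportion of 19.99% against the true 20%. Death therefore does not bias the proportion; unequal follow-up does. The last column shows why plain Kaplan-Meier with deaths censored is not the remedy: it errs upward.

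**Between arms.** At equal hazards, moving r from 15% to 25% changes the crude figure by 1.0 to 1.4 percentage points. That is small beside the interval width: the exact 95% interval for 5/23 (21.7%) is 7.5% to 43.7%.

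**Time to progression.** If deaths without progression are censored and make up 25%, 50% or 75% of first events, then with a median PFS of 5.6 months the 12-month cumulative incidence is 58%, 39% or 19%, while 1 − Kaplan-Meier gives 67%, 52% or 31%. With a median PFS of 12 months and a 25% share, the pair is 38% and 41%.

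**The case against.** The strongest reply is that the named endpoint is incidence over treatment and follow-up, and that the crude proportion describes exactly that window; a 12-month risk is named nowhere. This is fair as far as it goes. But a window that differs between patients by a factor of four or more defines no risk that can be interpreted or compared with another study.

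A reader might infer that death as a competing event invalidates the AML proportion. It does not. With everyone followed to a common horizon or death, the proportion is the cumulative incidence. A fixed horizon with complete follow-up would also cure the problem.

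A reader might also infer that the plan's Kaplan-Meier analysis of time to progression is wrong. The documents do not establish that, because they neither define the endpoint nor say that deaths are censored. If it means PFS as defined in Section 6.2.1, MDS deaths are events and only other deaths are left to handle.

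Three further points stand:
- The cited medians are overall survival in patients with progressive disease, so they are only a rough guide to death without AML in this population.
- Observation ending at 84 days is an assumption. Some non-responders may continue, and follow-up is named though not scheduled.
- The replacement has limits. With 23 patients and the hazards above, only about 2 to 5 long-observed patients per arm remain event-free after day 84 (23 × 0.15 × 0.54 = 1.9 to 23 × 0.25 × 0.87 = 5.0). Censoring at the end of treatment is tied to non-response and may be informative.

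No between-arm test of the AML proportion is specified.

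**Conclusion.** The concern holds in a limited form. The planned AML proportion has no horizon and mixes observation times from about 84 to 364 days or more, so it understates the risk by any fixed time beyond the shortest follow-up. In the illustration, a true 12-month incidence of 20% would appear as about 8% to 12%. That size rests on assumed constant hazards and on observation ending at the safety visit; none of the hazards comes from the documents.

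For time to progression the finding is conditional: an undefined endpoint, with overstatement only if deaths are censored. These are secondary endpoints, and the two-stage response-rate decision in each arm does not change. The change is worth making because it is cheap and concerns the first secondary objective.

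**What to change.** In Section 8.4.2:
- Estimate AML transformation per arm from first dose by the cumulative incidence function (Aalen-Johansen), with death without AML as a competing event.
- Report it with 95% confidence intervals and numbers at risk at pre-stated times that follow-up supports: for example 6 months, and 12 months only if AML status is collected alongside survival follow-up.
- Keep the crude count as a descriptive line.
- Limit the sentence on patients who discontinue before response to response endpoints.
- For time to progression, either state that it is the PFS endpoint or, if deaths without progression are not events, use the same cumulative incidence estimator in place of Kaplan-Meier.

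Cost: mostly wording and standard software, since progression and death dates are already needed for PFS and OS. A 12-month value would also need AML status recorded after treatment ends, which the calendar does not now schedule. The interval would no longer be exact and would be wide at 23 patients per arm. Possible informative censoring at the end of treatment should be acknowledged in the report.
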